For any subscales, trial outcome indexes, or total scores, we also define the minimum completion rate as the number of patients who complete at least one item included in the subscale, TOI, or total score, respectively, in order to assess the extent to which sites successfully administer a form to patients, even if only minimal information on the form is collected and the form cannot be scored according to the missing data rules for the instrument.

The primary reason for not completing any of the PRO assessments for any assessment time point will be collected on the PRO Coversheet, to be filled out by the personnel administering PROs at each site. The reasons will be summarized in table format.

g. **PRO analyses:** Consistent with the design and to aid in clinical interpretation, the analysis of the primary endpoint of the Cycle 3 FACT BRM TOI will be conducted using multivariable linear regression analysis, adjusting for randomization stratification factors and the baseline FACT BRM TOI score as covariates. A window of +/- 2 weeks around the completion of cycle 3 will be allowed for inclusion of the FACT-BRM TOI in the final analysis. We will also conduct longitudinal modeling of the outcome measures over time, to assess whether the longitudinal results are consistent with the primary analysis. Power for the longitudinal analysis will be greater since the addition of all available FACT BRM TOI scores over time will provide more information. For longitudinal modeling, linear mixed models will be used, with random effects for intercepts and slopes and using both compound symmetric and unstructured correlation models. Covariates for longitudinal modeling will include treatment arm, assessment time, their interaction, the baseline score, as well as the randomization stratification variables and the baseline FACT BRM TOI score. Additionally, a treatment by time-squared interaction will be evaluated. These models are nested and so log-likelihood values will be compared using a Chi-squared tests with appropriate degrees of freedom to assess which model provides a best fit to the data. When summarizing results from models with the best fit, coefficients for the intercept, treatment arm, time point, and baseline score will be tabulated, along with 95% confidence intervals and nominal p-values. We will also plot scale and subscale means for groups of patients based on the number of time points that instruments were completed.

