Interpretation of Longitudinal Model Results: For models in which the simple linear model (no interaction) provides the best fit, the fitted models will have parallel trajectories for the treatment arms, representing a treatment effect that is constant over time. Significant non-zero treatment arm coefficients will indicate that one arm having higher endpoint values over time compared to the other arm.

Significant non-zero time coefficients will indicate upward or downward endpoint changes over time (depending on the sign of the coefficient).

Models with an interaction will indicate a differential treatment effect on PRO endpoints over time, so the trajectories will not be parallel. If a square interaction is significant, the differential treatment effect will be modeled as quadratic (i.e., non-linear or curved). With significant interactions, the main effect coefficients for treatment arm and time cannot be interpreted independently but must be considered in combination with the coefficients for the interaction terms.

h. **Power and sample size calculations:** The primary hypothesis for sample size calculation is that pembrolizumab is superior to IFN with respect to the cycle 3 TOI score. PRO will be collected and data analyzed on all patients on the trial, not a subset of patients.

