We do not have preliminary PRO data on the FACT-BRM TOI with pembrolizumab or IFN in this particular patient population (the trial has wider eligibility than prior trials). The follow-up standard deviation for the FACT-BRM TOI was 20 in a set of nearly 200 patients receiving IFN for renal cell carcinoma. (31) This is consistent with data from Trask et al. (2004) in a small series of patients receiving IFN for high risk melanoma. (32) Thus we assume a cycle 3 standard deviation of the FACT BRM TOI of 20, common between both arms. Using Yost (2005), the estimated minimally important difference for the FACT BRM TOI is 5-8 points. If the standard deviation is 20 points, this difference is consistent with clinically meaningful effect sizes of 0.25-0.33, using distribution-based methods and anchor-based methods, respectively, identified by Yost et al. (33) Given the sample size is large, power is based on identifying a small effect size of 0.25. It is assumed, conservatively, that with a median OS for non-long term survivors of 3.96 and a median RFS for non-long term survivors of 1.44 years, then by cycle 3, 5% of patients will drop out due to death, 12% due to worsening disease, and 3% for other reasons, producing an overall dropout rate of 20% at cycle 3. Further, an additional 10% patients are assumed to be non-adherent. Patients who drop out or are non-adherent are considered invaluable. Note that in power calculations, the 10% non-adherence rate reduces the nominal effect size by 10% (to 0.225), while the 20% dropout rate inflates the estimated sample size by a factor of $1/(1-0.2)$ or 25%. Using a 2-sided alpha=0.05 test and a two-arm normal design, and accounting for dropout and non-adherence as specified, there will be 94% power to detect the effect size difference of 0.25 between the two arms.

Power will be worse with a smaller sample size. For instance, a sample size of 260 patients (130 per arm) will provide 83% power for a notably higher standardized difference (difference between means / standard deviation) of 0.4, using the same parameters as specified above. This effect size corresponds to a minimally important difference of 8 points in the FACT BRM TOI at cycle 3 if the standard deviation is 20%, the upper limit of the range of the minimally important difference as indicated in Yost et al.

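### The longitudinal PRO analysis lets model selection supply the arm claim and lists no time-squared main effect: about 14% false arm claims per scale, and more if arm is coded 0/1 and both arms share a curved course

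*Combined protocol and SAP*

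**What the plan says.** The primary PRO analysis is fixed in Sections 11.8c and 11.8g: the Cycle 3 FACT-BRM TOI is compared between arms by linear regression, adjusted for the baseline score and the stratification factors. Longitudinal mixed models are then fitted to see whether the course over time agrees with that result. Section 11.8c also uses them for change over all time points in the TOI and in every secondary PRO endpoint.

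The covariates listed in 11.8g are arm, assessment time, their interaction, the baseline score and the stratification factors. The text continues: "Additionally, a treatment by time-squared interaction will be evaluated". A time-squared main effect is neither listed nor excluded. The model is chosen by fit: "These models are nested and so log-likelihood values will be compared using a Chi-squared tests with appropriate degrees of freedom". No threshold, order of testing or multiplicity rule is given. For the best-fitting model, "coefficients for the intercept, treatment arm, time point, and baseline score will be tabulated", with confidence intervals and p-values that the plan labels nominal.

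The paragraphs of Section 11.8 on interpreting the longitudinal results then say how each outcome is read. In the model without interaction: "Significant non-zero treatment arm coefficients will indicate that one arm having higher endpoint values over time". A model with an interaction is read as showing a differential treatment effect, and "If a square interaction is significant, the differential treatment effect will be modeled as quadratic". The same text adds that, once an interaction is significant, the arm and time coefficients have to be read jointly with the interaction coefficients.

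**The concern.** Three features combine.

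- **No fixed contrast.** An arm difference can be claimed from the arm term, the linear interaction or the quadratic interaction, depending on which model wins on the same data.
- **A missing lower-order term.** If arm x time-squared is fitted without time-squared and arm is coded 0/1, only the arm coded 1 can bend. A dip and recovery common to both arms then has to appear as an arm effect.
- **An incomplete table.** The listed coefficients leave out the interaction terms. In an interaction model the arm coefficient alone is the difference at time zero.

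At stake are the stated consistency check on the primary TOI result and the over-time analysis of all secondary PRO scales, repeated in the subgroups by planned control regimen. Some curvature in the mean course is plausible, because patients are assessed on treatment at Weeks 4 to 49 and again 24 and 48 weeks after stopping.

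**Working it through.** **1. The plan's own figure.** Section 11.8h gives "Thus we assume a cycle 3 standard deviation of the FACT BRM TOI of 20, common between both arms". It continues "Using a 2-sided alpha=0.05 test and a two-arm normal design, and accounting for dropout and non-adherence as specified", and concludes "there will be 94% power to detect the effect size difference of 0.25 between the two arms". Inputs: 1,240 eligible patients (Section 11.1), 1:1 allocation, 20% dropout, and effect size 0.25 diluted by 10% to 0.225. Patients per arm: 1,240 x 0.8 / 2 = 496. Power = Φ(0.225 x √(496/2) − 1.96) = Φ(3.54 − 1.96) = Φ(1.58) ≈ 94.3%. The stated 94% reproduces. It belongs to the fixed Cycle 3 test; the plan states no error rate for the longitudinal analysis.

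**2. Search alone.** Take M0 = arm + time, M1 = M0 + arm x time, M2 = M1 + arm x time-squared, with each step a 1-df likelihood-ratio test at 5% (an assumption, since no threshold is given). A false claim is counted if M1 or M2 is chosen, or if M0 is chosen and its arm term has p < 0.05. Three independent tests would give 1 − 0.95³ = 14.3%. Simulation with no arm difference and a linear course (496 per arm, 20,000 replicates) gives 14.1%: 5.0% quadratic, 4.9% linear interaction, 4.2% arm term.

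**3. Why coding matters.** In M2 the quadratic part of the mean is h·A·t². With A = 0 or 1, the arm coded 0 has a straight line and the arm coded 1 has curvature h. If both arms truly have curvature c, h estimates c and not the arm difference of zero. With A = −0.5 or +0.5, the two arms are given curvature −h/2 and +h/2. A shared c then pulls h equally in both directions and, with balanced arms and visits, h centres on zero.

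**4. Size with shared curvature, no arm difference.** Chance of any false arm claim for one scale. Assumptions not in the documents: intercept SD 14, slope SD 6 per year, residual SD 13 (total about 20), visits at Weeks 4, 13, 25, 37, 49, 73 and 97, and a purely quadratic shared departure from a straight line.

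| Shared departure (points) | As listed, 0/1 | As listed, centred | 0/1, time-squared in all models | One fixed contrast (visit average) |
|---|---|---|---|---|
| 0 | 14.1% | 14.8% | 14.2% | 4.9% |
| 0.5 | 22.6% | 14.2% | 14.4% | 5.0% |
| 1 | 47.2% | 14.8% | 14.1% | 4.9% |
| 2 | 94.4% | 14.3% | 14.1% | 4.8% |
| 5 | 100% | 14.3% | 14.4% | 5.0% |

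A less regular shape gives smaller figures. With 430 per arm, intercept SD 12, slope SD 6 per year, residual SD 13 and the same visits, a 2-point shared dip or step gives about 21–25% for any claim under 0/1 coding. A 5-point dip that recovers gives about 56%, and a 5-point step lasting until treatment ends about 75%. Five points is the lower end of the plan's minimally important difference of 5 to 8. Adding the time-squared main effect returns the quadratic test to about 5%.

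Fitted maximum-likelihood mixed models agree in direction. With the 5-point dip, arm x time-squared was significant in 51% without and 3% with the time-squared main effect (39 replicates). With a 3-point quadratic course, 19 of 20 data sets gave a false claim.

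**5. What restores 5%.** Adding time-squared while keeping the search leaves about 14%, or 10–13% if time-squared enters only together with its interaction. One contrast fixed in advance gives 4.7–5.3% (visit average), and a 3-df joint test of all arm terms with time-squared in the model gives 4.8–5.4%, at every curvature tried.

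**The case against.** The strongest reply is that the large rates rest on things the plan does not say. Arm coding is not stated, and with centred coding the excess from shared curvature disappears. Curve shape, variances and selection threshold are assumptions, and the answer moves a great deal with shape: a 2-point shared course gives 21–25% in one form and 94% in another. The common visit schedule is also a simplification. The follow-up questionnaires are tied to each patient's last treatment, so someone completing ipilimumab at Week 145 would give them near Weeks 169 and 193 (145 + 24 and 145 + 48). Nor need the arms dip alike: the Background cites Grade 3/4 toxicity of 12% for pembrolizumab, 64% for high-dose interferon and 43% for ipilimumab. All of this stands, and it makes the higher figures conditional.

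A reader might infer that the plan offers the time-zero difference as the treatment effect. It does not: the interpretation text says main effects must be read with the interaction terms. What remains is that the table as listed leaves those terms out. The plan also has observed means plotted with the fitted model overlaid, so a badly forced curve could be noticed.

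Finally, the p-values are called nominal, so no 5% guarantee is broken. That is true, but the interpretation text still turns significance into statements about the arms, and the roughly 14% from the search depends neither on coding nor on curvature.

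**Conclusion.** The point holds for the supportive longitudinal PRO analysis. Selecting the model by fit and then reading whichever arm term is significant gives about 14% false arm claims per scale, if each of the three tests is made at 5%. If arm is coded 0/1 and time-squared is omitted as listed, shared curvature raises this to about 21–25% for 2 points and 56–75% for 5 points under the assumed variances and visits, and higher for a purely quadratic course. With centred coding it stays at about 14%. The multiplicity from two correlation structures, many subscales and subgroups is not counted.

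Two stronger readings are not supported. A reader might infer that the plan is bound to report a shared dip as a treatment effect. That needs the omission, 0/1 coding and a curved mean together, and the text settles neither of the first two. A reader might also infer that the PRO conclusion as a whole is unsafe. The Cycle 3 TOI regression has a fixed contrast and is unaffected.

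**What to change.** In Section 11.8g:

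- Include the time-squared main effect whenever arm x time-squared is fitted, or model assessment time as categorical.
- Pre-specify, for each endpoint, one longitudinal arm contrast or one joint test of all arm terms, and drop the rule that the best-fitting model supplies the arm claim. The choice is the sponsor's; a visit-averaged difference is one example. Whether to average over on-treatment visits only or over all visits should be stated.
- Tabulate the interaction coefficients, or model-based arm differences with confidence intervals at named weeks.

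The first change alone is not enough, because the search would still leave about 10–14%. The cost is SAP wording and model code, with no extra data and slightly less power against a strictly linear arm difference.

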11.8 Quality of life (QOL data)

This pre-specified statistical analysis plan (SAP) is intended to describe the strategy, rationale, and statistical techniques that will be used to assess the patient-reported outcomes (PROs) data gathered in the **S1404** trial.

- a. **Objectives:** The key objective of the PRO analysis is to evaluate overall health-related quality of life (QOL) for patients with melanoma treated with physician/patient choice of either high-dose interferon alfa-2b or ipilimumab and MK-3475 (pembrolizumab).
- b. **Instruments:** The FACT-BRM measures quality of life domains important to patients treated with biological response modifiers (BRMs). The domains are represented by six sets of response items, four of which comprise the FACT-General (FACT-G) subscales including Physical Well-Being, Social/Family Well-Being, Emotional Well-Being, and Functional Well-Being; and two additional subscales specific to the FACT-BRM instrument, the BRM Physical Subscale, and the BRM Cognitive/Emotional subscale. Each subscale is derived from 6-7 items on the questionnaire, with responses given on a five-point Likert-type scale ranging from 0 to 4 (0 = not at all, 1 = a little bit, 2 = somewhat, 3 = quite a bit, and 4 = very much). The six subscales are also combined to form a single FACT-BRM total score. In addition, the FACT-BRM Trial Outcome Index (TOI) is derived from a subset of four of the subscales (Physical Well-Being, Functional Well-Being, BRM Physical, and BRM Cognitive/Emotional). Each FACT BRM subscale, the FACT BRM total score, and the FACT BRM TOI will all be analyzed. Scoring of the scales will follow the standard published metrics. For the FACT BRM, the higher the score, the better the quality of life.

The FACIT-D comprises the FACT-G and a symptom-specific subscale that measures quality of life specific to diarrhea. Like the FACT-BRM, the FACIT-D subscales is scored on a 5-point Likert-type scale ranging from 0 to 4, with higher scores indicating better quality of life. The FACIT-D subscales (distinct from the FACT-BRM subscales) and FACT-D total score will all be analyzed.

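### Section 11.8h: with the stated dropout and non-adherence, 260 patients give about 74% power, not 83%; the effect-size range and the named comparator also need reconciling

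*Combined protocol and SAP*

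**What the plan says.** All of the following is in section 11.8h unless another section is named.

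- **Standard deviation:** "Thus we assume a cycle 3 standard deviation of the FACT BRM TOI of 20, common between both arms".
- **Important difference:** "the estimated minimally important difference for the FACT BRM TOI is 5-8 points". The section continues: "If the standard deviation is 20 points, this difference is consistent with clinically meaningful effect sizes of 0.25-0.33". The main calculation uses 0.25.
- **Adjustments:** 10% non-adherence lowers the effect from 0.25 to 0.225, and 20% dropout inflates the sample size by 1/(1 − 0.2).
- **Main result:** "Using a 2-sided alpha=0.05 test and a two-arm normal design, and accounting for dropout and non-adherence as specified", power is put at 94% for an effect of 0.25.
- **Smaller-sample example:** "a sample size of 260 patients (130 per arm) will provide 83% power for a notably higher standardized difference" of 0.4. The text says the parameters are those already set out, and equates 0.4 with 8 points at this standard deviation.
- **Hypothesis used for sizing:** "pembrolizumab is superior to IFN with respect to the cycle 3 TOI score". The next sentence says that data from every trial patient will be analysed.
- **Objective (11.8a):** quality of life for patients "treated with physician/patient choice of either high-dose interferon alfa-2b or ipilimumab and MK-3475 (pembrolizumab"). Section 11.8e takes all eligible randomised patients as the analysis population.

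**The concern.** The main figure and the example are said to rest on one set of assumptions, so one recipe should return both. It returns the first and not the second. The example is there to show how much power is lost with fewer patients, and as printed it understates that loss.

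The other two points concern consistency. The section gives two standardised values, 0.33 and 0.4, for the top of the same range in points. It also names interferon as the comparator, while the analysis it describes pools interferon and ipilimumab patients. A reader could take a positive pooled result as a finding against interferon specifically, which the pooled comparison cannot establish.

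**Working it through.** **Inputs.** Two-sided alpha 0.05, SD 20, dropout 20%, effect multiplied by 0.9 (all 11.8h). Allocation is 1:1 (11.3). Section 11.8h gives no total for the main calculation, so I take the 1,240 eligible patients of 11.1, or 620 per arm, in line with the population in 11.8e.

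**Formula.** With n evaluable patients per arm and standardised difference d, power = Φ(d × √(n/2) − 1.96).

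**Step 1: the plan's main figure.**
- n = 620 × 0.8 = 496; d = 0.25 × 0.9 = 0.225.
- 0.225 × √248 − 1.96 = 3.543 − 1.96 = 1.583, so power is 94.3%.
- The stated 94% reproduces, which confirms the recipe.

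**Step 2: the same recipe for 260 patients.**
- n = 130 × 0.8 = 104; d = 0.4 × 0.9 = 0.36.
- 0.36 × √52 − 1.96 = 2.596 − 1.96 = 0.636, so power is 73.8%.
- An exact t-test calculation gives 73.4%. The stated figure is 83%.

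**Step 3: which omissions come close to 83%?**

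| Variant | n per arm | d | Power |
|---|---|---|---|
| Both adjustments, two-sided 0.05 | 104 | 0.36 | 73.8% |
| No dropout, effect reduced | 130 | 0.36 | 82.7% |
| Dropout, effect not reduced | 104 | 0.40 | 82.2% |
| Neither adjustment | 130 | 0.40 | 89.7% |
| Both adjustments, one-sided 0.05 | 104 | 0.36 | 82.9% |

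The one-sided variant contradicts the stated two-sided test and would make the main figure 97.1%. Among two-sided variants, only the one without dropout rounds to 83%. It is the same calculation as 260 patients evaluable at Cycle 3, which would need 260/0.8 = 325 randomised.

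**Step 4: effect-size range.** 5/20 = 0.25 and 8/20 = 0.40. A value of 0.33 at SD 20 is 0.33 × 20 = 6.6 points. Only the upper end conflicts.

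**Step 5: comparator.** The 94% reproduces in step 1 with all 1,240 patients, that is, with the whole control arm. This agrees with 11.8a, 11.8e and the sentence in 11.8h about analysing every trial patient. The one place that says otherwise is the sizing hypothesis, which mentions interferon only.

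**The case against.** **The example may mean 260 completers.** Dropout would then already be removed and 82.7% would be right. That is possible, but the text gives 260 as a sample size and says the earlier parameters apply, and dropout is one of them. At the least, the denominator needs stating.

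**A reader might infer that omitted dropout is the only explanation.** The documents do not show this: omitting the effect reduction instead gives 82.2%, which is also close. The discrepancy does not depend on the cause.

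**A reader might infer that 74% is the power of the planned analysis.** It is not. The analysis in 11.8g adjusts for baseline TOI and the stratification factors, whereas 11.8h uses a simple two-arm calculation. No baseline-to-Cycle 3 correlation is given. If it were 0.3, 0.45 or 0.5 (my assumption), dividing d by √(1 − r²) would give about 78%, 83% or 85% with 104 per arm. This objection stands: what is wrong is the result reported for the simple calculation.

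**The value 0.33 may come from the cited study of meaningful change on the FACT-BRM.** That cannot be checked here. The sentence nevertheless ties it to 5 to 8 points at SD 20, which conflicts with the section's own 0.4.

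**A reader might infer that the primary quality-of-life comparison is against interferon and is underpowered.** With 310 interferon patients, power would be 70.7% within the interferon-declared stratum (248 evaluable per arm, d = 0.225), or 82.5% for all 620 pembrolizumab patients against those 310. But the plan makes no such comparison primary. The 310/310 split is assumed in 11.7b only for the precision of toxicity rates, and 11.8g already lists analyses by declared control regimen as secondary.

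**Conclusion.** The 83% is wrong as written. Under the section's own assumptions, 260 randomised patients give about 74% power at a standardised difference of 0.4, 9 points lower. This rests on the two-sided 5% test, SD 20, 20% dropout and 10% effect reduction that the section states. The 94% is correct for pembrolizumab against the randomised control arm, taking 1,240 eligible patients.

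The upper end of the effect-size range contradicts the section's own conversion of 8 points, but power is based on 0.25, so no power figure changes. The interferon-only wording is a mismatch of scope and not an arithmetic error.

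The practical effect is small. Quality of life is an additional objective (1.3c), and the 260-patient case is an illustration that sets no sample size or decision rule.

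**What to change.** Three edits to 11.8h:

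1. Change 83% to 74%. Alternatively, keep 83% and state that 260 is the number evaluable at Cycle 3, which corresponds to about 325 randomised.
2. Reconcile the effect-size range with the section's own conversion. If it is meant to express 5 to 8 points at SD 20, the upper end should be 0.40. If 0.33 is the cited study's figure, say so and do not equate it with 8 points at SD 20.
3. State the sizing hypothesis as superiority of pembrolizumab over the randomised control arm (high-dose interferon or ipilimumab).

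No power figure for the declared-regimen strata needs to be added. The cost is wording only, with no change to sample size, data collection or analysis.
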